9.3.5 EXTRACRANIAL RESPONSE RATE

Proprietary Information of MD Anderson

The best achieved extracranial objective response rate will be reported for each patient. The frequency of extracranial objective response will be reported overall and within each treatment group.

9.3.6 DURATION OF RESPONSE

In patients who achieve extracranial, partial response (PR) or complete response (CR) via RECIST 1.1 criteria, the time from date of first imaging identifying PR or CR until the date of first imaging identifying progressive disease is noted will be recorded. Duration will be calculated utilizing the Kaplan-Meier method with reporting of the median and range overall and within each treatment group.

9.3.7 STEROID REQUIREMENTS

We will record and report steroid requirements for symptom management overall and within each treatment group. Patients who require at least 4 mg of dexamethasone/day for symptom management will be considered as requiring high dose steroids.

9.3.8 OTHER ENDPOINTS

Descriptive analysis will be provided to summarize the serum, tissue and imaging markers. The relationship between the markers and response and/or toxicities may be evaluated using Kruskal-Wallis test for continuous markers and Fisher's exact test for discrete markers, when appropriate. The correlation between the serum/tissue markers and imaging parameters or between any two markers may also be assessed using Spearman correlation. Given the size of the study, these analysis are exploratory in nature.

Other statistical analysis methods may be applied when fit.

The Principal Investigator is responsible for completing toxicity/efficacy summary reports and submitting them to the IND office Medical Affairs and Safety Group for review. These should be submitted as follows:

- Phase I:

After the first 3 evaluable patients, complete 4 weeks of study treatment, and every 3 evaluable patients thereafter, IND Office approval must be obtained prior to advancing/changing dose levels.

- Phase II:

After the first 10 evaluable patients(including the six treated at RP2D from phase I) complete 4 weeks of study treatment, and every 5 patients thereafter. Also, a toxicity report will be submitted per cohort.

A copy of the summary report should be placed in the Principal Investigator's Regulatory Binder under "sponsor correspondence".

10.0 ASSESSMENT OF SAFETY

10.1 ADVERSE EVENT ASSESSMENT AND REPORTING

Proprietary Information of MD Anderson

An adverse event is defined as any untoward medical occurrence in a patient or clinical investigation subject administered a pharmaceutical product and which does not necessarily have to have a causal relationship with this treatment. An adverse event can therefore be any unfavorable and unintended sign (including an abnormal laboratory finding, for example), symptom, or disease temporally associated with the use of a medicinal product or protocol - specified procedure, whether or not considered related to the medicinal product or protocol specified procedure. Any worsening (i.e., any clinically significant adverse change in frequency and/or intensity) of a preexisting condition that is temporally associated with the use of the investigational products is also an adverse event.

Changes resulting from normal growth and development that do not vary significantly in frequency or severity from expected levels are not to be considered adverse events. Examples of this may include, but are not limited to, teething, typical crying in infants and children and onset of menses or menopause occurring at a physiologically appropriate time.

Adverse events may occur during clinical trials or as prescribed in clinical practice, from overdose (whether accidental or intentional), from abuse and from withdrawal.

Progression of the cancer under study is not considered an adverse event.

From the time of initial protocol treatment through 30 days following cessation of treatment, all adverse events must be recorded. Such events will be recorded at each examination in the medical record. The reporting timeframe for adverse events meeting any serious criteria is described in Section 8.13. The principal investigator will make every attempt to follow all subjects with non-serious adverse events for outcome.

The principal investigator (or physician designee) is responsible for verifying and providing source documentation for all adverse events and assigning the attribution for all adverse events for subjects enrolled.

An principal investigator who is a qualified physician will evaluate all adverse events according to the NCI Common Terminology for Adverse Events (CTCAE), version 5.0. Any adverse event which changes CTCAE grade over the course of a given episode will have each change of grade recorded on the adverse event case report forms/worksheets.

All adverse events regardless of CTCAE grade must also be evaluated for seriousness.

Severity of the adverse events (AEs) -The severity of the adverse events (AEs) will be graded according to the **National Cancer Institute Common Terminology Criteria for Adverse Events (NCI CTCAE) V.5.0.** Events not included in the NCI CTCAE will be scored as follows:

General grading:

- **Grade 1:** Mild: discomfort present with no disruption of daily activity, no treatment required beyond prophylaxis.

Proprietary Information of MD Anderson

- **Grade 2:** Moderate: discomfort present with some disruption of daily activity, require treatment.
- **Grade 3:** Severe: discomfort that interrupts normal daily activity, not responding to first line treatment.
- **Grade 4:** Life Threatening: discomfort that represents immediate risk of death

For studies in which multiple agents are administered as part of a combination regimen, the principal investigator may attribute each adverse event causality to the combination regimen or to a single agent of the combination. In general, causality attribution should be assigned to the combination regimen (i.e., to all agents in the regimen). However, causality attribution may be assigned to a single agent if in the principal investigator's opinion, there is sufficient data to support full attribution of the adverse experience to the single agent.

All Adverse Events will be reported to regulatory authorities, IRB/IECs and principal investigators in accordance with all applicable global laws and regulations.

Attribution - the determination of whether an adverse event is related to a medical treatment or procedure.

- **Definite** - the adverse event is clearly related to the investigational agent(s).
- **Probable** - the adverse event is likely related to the investigational agent(s).
- **Possible** - the adverse event may be related to the investigational agent(s).
- **Unlikely** - The adverse event is doubtfully related to the investigational agent(s).
- **Unrelated** - The adverse event is clearly NOT related to the investigational agent(s).

Recommended Adverse Event Recording Guidelines

Attribution	Grade 1	Grade 2	Grade 3	Grade 4	Grade 5
Unrelated	Phase I	Phase I	Phase I	Phase I	Phase I
			Phase II	Phase II	Phase II
				Phase III	Phase III
Unlikely	Phase I	Phase I	Phase I	Phase I	Phase I
			Phase II	Phase II	Phase II
				Phase III	Phase III
Possible	Phase I	Phase I	Phase I	Phase I	Phase I
	Phase II	Phase II	Phase II	Phase II	Phase II
		Phase III	Phase III	Phase III	Phase III
Probable	Phase I	Phase I	Phase I	Phase I	Phase I
	Phase II	Phase II	Phase II	Phase II	Phase II
		Phase III	Phase III	Phase III	Phase III

Proprietary Information of MD Anderson

Definitive	Phase I Phase II Phase III				
-------------------	----------------------------------	----------------------------------	----------------------------------	----------------------------------	----------------------------------

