9.2 PHASE II

The purpose of phase II part is to estimate the time to intra-cranial progression and overall survival time. In this part, we will enroll up to additional 24 patients into RP2D over the course of 12-18 months. The 6 patients treated at RP2D from phase I part of the study will be included in the Phase II part, thus resulting in a total of 30 patients at RP2D by the end of the study, with the goal of having 10 patients with each of melanoma, NSCLC, and breast cancer. This phase II part is designed to collect data for future larger studies. Specifically, we would like to estimate time to intracranial progression considering death as a competing risk and overall survival time using Kaplan-Meier method, both with 95% confidence interval.

Two dose limiting toxicities (DLT) will be monitored separately: intracranial and extracranial DLTs. If there is a high chance that probability of intracranial DLT is found to be $> 15\%$, i.e., $\text{Pr}(\text{intra-cranial DLT Rate} > 15\% | \text{Data}) > 70\%$, or the extra-cranial DLT rate of higher than 30% , i.e., $\text{Pr}(\text{extra-cranial DLT Rate} > 30\% | \text{Data}) > 70\%$, then the regimen will be considered too toxic at current dose. Results should be discussed with EMD Serono to decide if further enrollment should be started at a lower dose level. Protocol will be amended if necessary. The window for DLT evaluation will be at 4 weeks after the start of the treatment.

Given these rules and the prior for intra-cranial DLT toxicity rate as $\text{beta}(0.15, 0.85)$ and extra-cranial DLT toxicity rate as $\text{beta}(0.3, 0.7)$, we claim a dose level too toxic if any of the following happens.

Number of patients with intra-cranial DLTs/total of number of patients treated $\geq 3/10, 4/15, 5/20, 5/25, 6/30$; or

Number of patients with extra-cranial DLTs/total of number of patients treated $\geq 4/10, 6/15, 8/20, 9/25, 11/30$.

The operating characteristics based on the toxicity stopping rules for 30 patients are in Table 4. The Bayesian toxicity monitoring rule are calculated by the online Shiny application Bayesian Toxicity Monitoring using posterior probability developed by Department of Biostatistics. The operating characteristics were evaluated using codes written by statistical collaborator [name].

Table 4: Operating Characteristics (5,000 simulations)

True Intracranial DLT Rate	True Extracranial DLT Rate	P (Stop Early)	Average of Expected Sample Size
0.05	0.1	0.03	29

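### Section 10.1 requires all adverse events to be recorded, but its recommended table omits grade 1–2 Unrelated and Unlikely events in Phase II; if the table governs the eCRF, low-grade not-related rates at the RP2D are understated

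*Combined protocol and SAP*

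**What the plan says.** **Section 10.1, text.** The recording duty is general: "From the time of initial protocol treatment through 30 days following cessation of treatment, all adverse events must be recorded". The next sentence gives a location: "Such events will be recorded at each examination in the medical record". The investigator, or a delegated physician, "is responsible for verifying and providing source documentation for all adverse events and assigning the attribution for all adverse events for subjects enrolled". For grade changes, the section names the case report forms or worksheets as the place of entry: "Any adverse event which changes CTCAE grade over the course of a given episode will have each change of grade recorded on the adverse event". None of these sentences is limited by grade, attribution or phase.

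**Section 10.1, table.** Under the title "Recommended Adverse Event Recording Guidelines" there are five attribution rows and five grade columns. Phase I appears in every cell. Phase II appears at every grade for Possible, Probable and Definitive, but only at grades 3 to 5 for Unrelated and Unlikely. The table does not say whether it refers to the medical record or the eCRF.

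**Section 9.2.** On the expansion: "we will enroll up to additional 24 patients into RP2D over the course of 12-18 months". On the carry-over: "The 6 patients treated at RP2D from phase I part of the study will be included in the Phase II part". The plan then gives the size of the combined set: "thus resulting in a total of 30 patients at RP2D by the end of the study".

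**Section 9.3.3.** Toxicities are to be summarised by grade, relationship and time on treatment, for each dose in each group. There is no grade or attribution cut-off and no separation of phase I from phase II patients.

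**Section 11.3.1.** Study data are entered in eCRFs in the trial database.

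**The concern.** The sentence and the table give different answers for a grade 1 or 2 event in a phase II patient that the investigator judges unrelated or unlikely to be related. The document does not say which prevails. It also does not say which phase label applies to the six patients who count in both parts.

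This matters because the RP2D set combines patients from both parts. Section 3.0 gives better characterisation of the safety profile as a purpose of the expansion, and Section 4.2 lists safety and tolerability of the combination as a secondary objective. The trial has no control arm, so attribution is an individual judgement, and the table makes that judgement decide whether a low-grade event is recorded at all. An event left out of the database cannot later be re-attributed from it if a pattern emerges.

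**Working it through.** **1. The RP2D set.** From Section 9.2, 6 + 24 = 30, which reproduces the plan's total. Under the table, 6/30 = 20% of the set would have full capture and 24/30 = 80% (at full enrolment) the narrower rule. By Section 9.3.8 the first phase II toxicity report covers 10 evaluable patients including those six. At that point the split would be 6 and 4.

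**2. The cells that differ.** There are 5 attributions × 5 grades = 25 cells. The phases differ in 2 attributions (Unrelated, Unlikely) × 2 grades (1, 2) = 4 cells.

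**3. Can the two instructions be read together?** One attempt is that all events go in the medical record and the table sets what goes on the case report form. Take an unrelated event in a phase II patient that moves from grade 1 to grade 2. The grade-change sentence requires each change on the case report forms or worksheets; the table has no Phase II entry for either grade. The conflict therefore remains. Even if worksheets are read as source papers, the database would hold these events for 6 patients and not for up to 24.

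**4. Size if the table governs the eCRF.** Let q be the share of patients whose only occurrence of a given event is grade 1–2 and Unrelated or Unlikely. The documents give no value, so q is an assumption, taken as equal in both groups.

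Shown in the not-related low-grade rows: (6 × q + 24 × 0)/30 = 0.2q.

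| Assumed q | Expected patients missed (24q) | Pooled table shows (0.2q) |
|---|---|---|
| 10% | 2.4 | 2% |
| 30% | 7.2 | 6% |
| 50% | 12.0 | 10% |

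For an all-causality any-grade total with true rate p that includes q, the table shows (6p + 24(p − q))/30 = p − 0.8q. With p assumed at 40% and q at 10%, 20% or 30%, this gives 32%, 24% or 16%. A patient with another recordable occurrence of the same event (grade 3+, or at least possibly related) is still counted and does not belong in q.

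**5. What does not move.** The stopping boundaries in Section 9.2 were recomputed. With prior Beta(a, b) and r DLTs in n patients, the boundary is the smallest r for which Pr(rate > t) under Beta(a + r, b + n − r) exceeds 0.70.

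- Intracranial, Beta(0.15, 0.85), t = 15%: 3/10, 4/15, 5/20, 5/25, 6/30. At n = 10 the posterior probability is 0.848 for 3 events and 0.594 for 2.
- Extracranial, Beta(0.3, 0.7), t = 30%: 4/10, 6/15, 8/20, 9/25, 11/30. At n = 10 it is 0.720 for 4 events and 0.465 for 3.

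All ten match the plan. By Section 9.1, intracranial DLTs are grade 3 or higher, extracranial DLTs are grade 3 or higher and related, and the combined liver criterion needs attribution to study drug. None of these falls in the four cells.

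**The case against.** The strongest reply is that there is no contradiction. The mandatory sentence is followed at once by one that places recording in the medical record, while the table is only recommended. The table also carries Phase III entries in a phase I/II trial, which suggests that it is standard text. If the mandatory sentence prevails, all 30 patients share one standard. Sections 8.1.1 and 8.1.2 (new clinically significant findings recorded as adverse events) and 11.3.2 (toxicities evaluated throughout) make no exception by phase.

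This stands in part: unequal capture is conditional, not established. It does not remove the ambiguity, because the grade-change sentence does not fit a source-only reading, and a recommendation with no stated precedence leaves the choice to site staff.

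Other parts of the reply stand fully:

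- Section 9.2 combines the 30 patients for time to intracranial progression, overall survival and DLT monitoring. The route to adverse event rates is Section 9.3.3.
- A reader might infer that an artificial phase I versus phase II difference would be reported. No such comparison is planned.
- A reader might infer that neurologic, visual or bleeding events would routinely be lost. The documents do not support this. Section 10.1 generally attributes events to the whole regimen, and Possible requires only that an event may be related. Section 6.2.3 treats bleeding as an identified risk of bintrafusp alfa. The NANO scale and eye examinations are scheduled regardless of attribution.

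**Conclusion.** The point holds as an unresolved conflict within Section 10.1, with a conditional effect. If the table governs the eCRF, 6 of 30 RP2D patients have full capture and up to 24 do not. The low-grade not-related rows then show about 0.2q, and all-causality any-grade totals fall short by about 0.8q. These sizes rest on an assumed q that is equal in both groups, on 24 patients being enrolled, and on the table being followed throughout.

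A reader might go further and conclude that the plan does mix two standards, or that its safety monitoring is compromised. The documents support neither. The table is only recommended, and DLT counts, stopping boundaries, grade 3+ events (including the grade 3+ intracranial toxicity endpoint), serious events, which are reported regardless of attribution, and events at least possibly related are captured alike in both phases. The primary analyses are untouched. It is still worth settling before phase II data entry, because low-grade events not entered at the time are hard to recover consistently.

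**What to change.** State in Section 10.1 that the all-events sentence governs the eCRF for every patient, and use the table's Phase I entries (all grades, all attributions) throughout this trial. The cost is one clarifying sentence and some extra data entry for up to 24 patients, whose events Section 10.1 already requires to be graded, attributed and documented in source.

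If the table is kept, then in Sections 10.1 and 9.3.3:

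- pool only events captured in both phases, namely grade 3+ of any attribution and any grade at least possibly related;
- say which rule applies to the six carried-over patients;
- show grade 1–2 Unrelated or Unlikely events for the phase I patients separately, with their own denominator.

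This alternative saves the data entry but gives up an all-causality any-grade rate for the 30.

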4.2 SECONDARY OBJECTIVES

- Intracranial progression 4, 8, 12, 16 weeks and every 8 weeks thereafter.
- Intracranial objective response rate as measured by RANO-BM, iRANO, and RECIST 1.1.
- Time to second intracranial progression after Salvage SRS
- Overall survival rate at 24, 52 and 68 weeks.
- Frequency of grade 3+ intracranial toxicities at 4, 12, 24, 36, 52, and 68 weeks. Frequency of extracranial progression and response rate at 8, 16, 24, every 8 weeks.
- Frequency of neurocognitive decline 12, 24, 36 weeks (optional). Changes in neurocognitive function and health-related quality of life.
- Dose, duration and frequency of steroid use for symptomatic management.
- Evaluation of safety and tolerability of pimasertib/bintrafusp alfa combination

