8.0 SCHEDULE OF ASSESSMENTS

TABLE 3 SCHEDULE OF ASSESSMENTS

Trial Period:	Screening Phase	Treatment Cycles ^a										End of Treatment	Post-Treatment		
		To be repeated beyond 8 cycles				Discontinuation				Safety Follow-up	Follow Up Visits ^b				
Treatment Cycle/Title:	Screening	C1 D1	C1 D15	C2 D1	C2 D15	3	4	5	6	7	8				
Scheduling Window (Days):	-28 to -1			± 3		± 3	± 3	± 3	± 3	± 3	± 3	At time of Discontinuation	30 days post discontinuation ± 7	Every 6 weeks post discontinuation ± 7	Every 12 weeks ± 7
Administrative Procedures															
Informed Consent	X														
Inclusion/Exclusion Criteria	X														
Demographics and Medical History	X														
Prior and Concomitant Medication Review	X	X	X	X	X	X	X	X	X	X	X	X			
Trial Treatment Administration ^c		X	X	X	X	X	X	X	X	X	X				

Trial Period:	Screening Phase	Treatment Cycles ^a										End of Treatment	Post-Treatment			
		To be repeated beyond 8 cycles														
Treatment Cycle/Title:	Screening	C1	C1	C2	C2	3	4	5	6	7	8	Discontinuation	Safety Follow-up	Follow Up Visits ^b	Survival Follow-Up ^p	
		D1	D15	D1	D15			± 3	± 3	± 3	± 3					
Scheduling Window (Days):	-28 to -1												At time of Discontinuation	30 days post discontinuation ± 7	Every 6 weeks post discontinuation ± 7	Every 12 weeks ± 7
Post-study anticancer therapy status															X	X
Survival Status																X
Clinical Procedures/Assessments																
Review Adverse Events			X	X	X	X	X	X	X	X	X	X	X	X	X	X
Physical Examination	X		X	X	X	X	X	X	X	X	X	X	X			X
Vital Signs, Weight, and Height ⁿ	X		X	X	X	X	X	X	X	X	X	X	X			X
Electrocardiogram (12-Lead ECGs)	X															
ECHO/MUGA	X			X			X		X		X		X			
Ophthalmological Exam ^l	X						X		X		X		X			

Trial Period:	Screening Phase	Treatment Cycles ^a										End of Treatment	Post-Treatment		
		To be repeated beyond 8 cycles											Safety Follow-up	Follow Up Visits ^b	Survival Follow-Up ^p
Treatment Cycle/Title:	Screening	C1 D1	C1 D15	C2 D1	C2 D15	3	4	5	6	7	8	Discontinuation			
		± 3	± 3	± 3	± 3	± 3	± 3	± 3	± 3	± 3	± 3	At time of Discontinuation			
Scheduling Window (Days):	-28 to -1												30 days post discontinuation ± 7	Every 6 weeks post discontinuation ± 7	Every 12 weeks ± 7
ECOG Performance Status	X	X	X	X	X	X	X	X	X	X	X	X		X	X
Neuro-function (NANO)	X	X		X		X	X	X	X	X	X	X			
Neuropsych Testing ^o /Neurocognitive Testing	X					X									
Laboratory Procedures/Assessments: analysis performed by LOCAL laboratory															

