Pregnancy Test – Urine or Serum -HCG ^d	X			X		X	X	X	X	X	X	X			
Coagulation ^e	X														
CBC with Differential ^k	X	X	X	X	X	X	X	X	X	X	X	X		X	
CMP ^m	X	X	X	X	X	X	X	X	X	X	X	X		X	
Urinalysis	X			X		X	X	X	X	X	X	X			

Trial Period:	Screening Phase	Treatment Cycles ^a								End of Treatment	Post-Treatment				
		To be repeated beyond 8 cycles				Discontinuation					Safety Follow-up	Follow Up Visits ^b	Survival Follow-Up ^p		
Treatment Cycle/Title:	Screening	C1 D1	C1 D15	C2 D1	C2 D15	3	4	5	6	7	8				
Scheduling Window (Days):	-28 to -1			± 3		± 3	± 3	± 3	± 3	± 3	± 3	At time of Discontinuation	30 days post discontinuation ± 7	Every 6 weeks post discontinuation ± 7	Every 12 weeks ± 7
Lactate dehydrogenase (LDH)	X			X		X	X	X	X	X	X	X			
T3, FT4 and TSH	X	X				X		X		X		X			
Creatinine Phosphokinase	X	X		X		X	X	X	X	X	X	X			
HIV, HBV, HCV Testing	X														
Efficacy Measurement															
Tumor Imaging & Assessment of disease: MRI ^f	X			X		X	X	X	X	X	X	X			
Tumor Imaging & Assessment of disease: CT's ^f	X					X		X		X					
Tumor Biopsies/Archival Tissue Collection/Correlative Studies Blood															

Trial Period:	Screening Phase	Treatment Cycles ^a								End of Treatment	Post-Treatment				
		To be repeated beyond 8 cycles				Discontinuation					Safety Follow-up	Follow Up Visits ^b	Survival Follow-Up ^p		
Treatment Cycle/Title:	Screening	C1 D1	C1 D15	C2 D1	C2 D15	3	4	5	6	7	8				
Scheduling Window (Days):	-28 to -1			± 3		± 3	± 3	± 3	± 3	± 3	± 3	At time of Discontinuation	30 days post discontinuation ± 7	Every 6 weeks post discontinuation ± 7	Every 12 weeks ± 7
Archival Tissue ^g	X														
Serial Biopsy ^h	X			X			X								
Blood/Tissue Collection	X			X		X	X	X	X	X	X				
Correlative Studies ^j	X			X			X				X				
PK and ADA		X		X		X		X			X		X		
CSF ⁱ (optional)	X	X				X									

- a Cycles are 4 weeks (28 days) in duration
- b Patients who discontinue trial treatment for reasons other than disease progression will move into the Follow-Up phase. Patients will be seen every 6 weeks for the first year, then every 12 weeks thereafter up to 2 years.
- c M7824 1200 mg every 2 weeks. Pimasertib will be administered at 60mg twice daily. (30 to 60 mg depending on phase)
- d See Page 78 if a woman of child-bearing potential becomes pregnant while on study. Negative pregnancy test within 3 days prior to initiation of dosing and continuation of birth control for 120 days after last dose of drug.

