8.15 POST STUDY DRUG FOLLOW UP

In this study, clinical benefit rate is the primary endpoint of the study. Post study follow-up is of critical importance and is essential to preserving subject safety and the integrity of the study.

Subjects who discontinue study drug must continue to be followed for collection of outcome and/or survival follow-up data as required by phone every 12 weeks until death or the conclusion of the study.

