 - **All life-threatening or fatal events**, that are unexpected, and related to the study drug, must have a written report submitted within 24 hours (next working day) of knowledge of

Proprietary Information of MD Anderson

- the event to the Safety Project Manager in the IND Office.
- Unless otherwise noted, the electronic SAE application (eSAE) will be utilized for safety reporting to the IND Office and MDACC IRB.
- The electronic SAE application (eSAE) will be utilized for safety reporting to the IND Office and MDACC IRB.
- Serious adverse events will be captured from the time of the first protocol-specific intervention, until 90 days following cessation of treatment, or 30 days following cessation of treatment if the participant initiates new anticancer therapy, whichever is earlier unless the participant withdraws consent. Serious adverse events must be followed until clinical recovery is complete and laboratory tests have returned to baseline, progression of the event has stabilized, or there has been acceptable resolution of the event.
- Additionally, any serious adverse events that occur after the 90 days following cessation of treatment, or 30 days following cessation of treatment if the participant initiates new anticancer therapy that are related to the study treatment must be reported to the IND Office. This may include the development of a secondary malignancy.

Reporting to FDA:

- Serious adverse events will be forwarded to FDA by the IND Sponsor (Safety Project Manager IND Office) according to 21 CFR 312.32.

It is the responsibility of the PI and the research team to ensure serious adverse events are reported according to the Code of Federal Regulations, Good Clinical Practices, the protocol guidelines, the sponsor's guidelines, and Institutional Review Board policy.

Pregnancy and Reporting

If, following initiation of the investigational product, it is subsequently discovered that a study subject is pregnant or may have been pregnant at the time of investigational product exposure, including during at least 6 half-lives after product administration, the investigational product will be permanently discontinued in an appropriate manner (eg, dose tapering if necessary for subject safety). The investigator must immediately notify EMD Serono of this event via the Pregnancy Surveillance Form in accordance with SAE reporting procedures within 24 hours.

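### Grade 3+ intracranial toxicity is to be reported to week 68, but the adverse event capture rules conflict and, apart from Table 3, none reaches week 68 for all patients

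*Combined protocol and SAP*

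**What the plan says.** The endpoint, in Section 4.2 and the Trial Summary, is "Frequency of grade 3+ intracranial toxicities at 4, 12, 24, 36, 52, and 68 weeks". Neither place limits it to time on treatment.

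The rules that would feed it are spread over several sections:

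- **Section 10.1, all adverse events:** "From the time of initial protocol treatment through 30 days following cessation of treatment, all adverse events must be recorded". For serious events it refers the reader to Section 8.13, which deals with withdrawal and gives no reporting window.
- **Section 10.2, serious events:** "Serious adverse events will be captured from the time of the first protocol-specific intervention, until 90 days following cessation of treatment", or until 30 days if new anticancer therapy begins, whichever is earlier. Beyond that, "any serious adverse events that occur after the 90 days following cessation of treatment" (or after the 30 days, with new therapy) must still be reported if related to study treatment. No end date is set.
- **Table 3, schedule of assessments:** the row "Review Adverse Events" appears to be marked at every contact after screening, including the 6-weekly follow-up visits and the 12-weekly survival follow-up. Footnote p adds one safety call at 90 days.
- **Table 3, footnote b:** "Patients who discontinue trial treatment for reasons other than disease progression will move into the Follow-Up phase". For that group, "Patients will be seen every 6 weeks for the first year, then every 12 weeks thereafter up to 2 years".
- **Section 8.15:** "Subjects who discontinue study drug must continue to be followed for collection of outcome and/or survival follow-up data as required by phone every 12 weeks". Adverse events are not named.
- **Section 9.3.3:** toxicity is summarised descriptively, including by its timing within treatment. No denominator, censoring rule or handling of death is given for the week-68 frequency.

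**The concern.** A frequency at week 68 needs patients observed for the event up to week 68, or a stated rule for those who are not. The text of Section 10 ties capture to the end of treatment, while the endpoint runs on a clock that does not stop when treatment does. Table 3 seems to follow the endpoint's clock, so site staff have two instructions and no statement of which prevails.

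The gap would not fall at random. Patients who stop for progression have no 6-weekly visits, and their telephone follow-up is not described as collecting toxicity. They are also likely to start new therapy, which shortens serious-event capture to 30 days. Salvage SRS is part of the design (Sections 3.0 and 6.2.8), and radiation necrosis is named as a toxicity of interest in Section 4.3. Attribution in Section 10.1 is defined against the investigational agents. A late serious event put down to SRS could therefore be classed as unrelated and fall outside the open-ended clause in Section 10.2.

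At stake is whether the late points of a secondary safety endpoint can be read as frequencies at all.

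**Working it through.** The plan gives no figure to reproduce. The check compares dates and then sets the rules side by side.

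**Inputs.** Endpoint horizon 68 weeks (Section 4.2). All-event window 30 days = 30/7 = 4.29 weeks after treatment (Section 10.1). Serious-event window 90 days = 90/7 = 12.86 weeks after treatment, with no new therapy (Section 10.2).

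**Step 1: how long a patient must stay on drug to be covered to week 68.**
- All events: 68 − 4.29 = week 63.7.
- Serious events: 68 − 12.86 = week 55.1.

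**Step 2: where capture ends for a given stopping week** (stopping week + 4.29, or + 12.86).

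| Treatment stops | All events to week | Short of week 68 by | Serious events to week | Short of week 68 by |
|---|---|---|---|---|
| 8 | 12.3 | 55.7 | 20.9 | 47.1 |
| 24 | 28.3 | 39.7 | 36.9 | 31.1 |
| 52 | 56.3 | 11.7 | 64.9 | 3.1 |

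For a patient who stops at week 24, all-event recording ends before the week 36, 52 and 68 time points. The serious-event window just passes week 36 and misses the other two.

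**Step 3: does another rule close the gap?** The 6-weekly visits exclude patients who stop for progression. Section 8.15 does not name toxicity. The 90-day call is a single contact. Events of clinical interest (Section 10.3) share the 90/30-day window, and those listed are overdose and a liver-test pattern, not intracranial toxicity. Only the Table 3 row could close it. That row has 14 marks, and there are 14 columns after screening: 10 treatment visits, discontinuation, safety follow-up, follow-up visits and survival follow-up. The alignment is inferred from this count, because the table text is broken.

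**Step 4: what remains if Sections 10.1 and 10.2 prevail.**
- Non-serious grade 3+ intracranial events after 30 days.
- Serious intracranial events judged unrelated to study drug after 90 days, or after 30 days with new therapy.

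**Step 5: illustration only.** The documents give no expected treatment duration. Assume exponential time on treatment with median m weeks, everyone alive to week 68 and no new therapy. The share of patients covered to week 68 is then exp(−ln 2 × 63.7/m) for all events and exp(−ln 2 × 55.1/m) for serious events. Out of 30 patients:

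| Assumed m | All events | Serious events |
|---|---|---|
| 8 | 0.1 | 0.3 |
| 16 | 1.9 | 2.8 |
| 24 | 4.8 | 6.1 |
| 52 | 12.8 | 14.4 |

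These count patients whose required capture runs to week 68. They do not count missed events. Because deaths are ignored, some of the uncovered patients would not be at risk by then.

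**The case against.** The strongest reply is that the protocol already collects these events. If Table 3 is read as it appears, adverse events are reviewed at every post-treatment contact. Section 10.1 sets what must be recorded and does not forbid later recording. Serious events run to 90 days, and related ones are reportable without limit. All of that stands. A reader might infer that adverse events are recorded only to 30 days and that late toxicity is therefore undercounted, but the documents do not support that. What they show is conflicting instructions and a loss that depends on which one is followed.

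A reader might also infer that any patient who progresses and receives SRS drops out of capture. That is not so. Section 6.2.8 lets such patients stay on systemic therapy, Section 6.2.4 allows resumption after a hold, and Section 8.10 permits treatment past progression under conditions. Those who continue remain inside the window, so the exposure is confined to permanent discontinuation.

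Finally, Section 9.3.3 could be read as planning only an on-treatment summary. If that is the intent, the endpoint in Section 4.2 does not say so.

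**Conclusion.** The inconsistency is real and should be resolved. Apart from Table 3, no rule carries grade 3+ intracranial capture to week 68 for all patients. All-event recording gets there only for patients on drug to about week 63.7, and serious-event capture only for those on drug to about week 55.1. Frequencies at weeks 36 to 68 are at risk of being biased low under two conditions: Sections 10.1 and 10.2 are followed over Table 3, and patients no longer under capture stay in the denominator.

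A reader might want a count of patients or events lost. The documents cannot supply one: treatment duration is not stated, and the illustration moves from almost none of 30 patients covered to nearly half, depending on the assumed median. The 4-week DLT definition and the stopping rules in Section 9.2 are unaffected.

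**What to change.** Reconcile Sections 10.1, 10.2, 8.15 and Table 3:

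- State that intracranial toxicities of grade 3 or higher are collected for every patient, whatever their seriousness or attribution, to week 68 or death, at the follow-up visits and 12-weekly calls already scheduled.
- Record the start date of any new anticancer therapy and the dates of any SRS, so that events can be read in context.
- Confirm the post-treatment marks in the Table 3 adverse event row, and correct the reference in Section 10.1 to Section 8.13.
- In Section 9.3.3, report cumulative incidence at the listed weeks with death as a competing risk and censoring at the last adverse event assessment.

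If the sponsor will not collect this, restrict the endpoint to the on-treatment plus safety window and say so in Section 4.2 and the Trial Summary.

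The cost is protocol wording and a small amount of extra data entry. Two limits remain. Some events after new therapy will be hard to attribute. Telephone contacts may also miss events that need imaging to detect, since scheduled MRI ends at progression or discontinuation, whichever is later.
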